6.5. Dose Interruption and Reduction

The following are the guidelines for dose interruption and/or reduction. If an AE is attributed to study drug, the investigator's discretion will be used to determine if the drug not attributed to the AE will be withheld based on the investigator's assessment of risk-benefit of withholding the study drug.

Subjects who experience Grade 3 or 4 neutropenia whilst on idelalisib treatment must have their neutrophil count measured weekly until resolution to \leq Grade 2, per Table 6.2.

An interruption of tirabrutinib and/or idelalisib administration of up to 2 weeks will be acceptable to allow for any reversal of toxicity between doses of tirabrutinib and/or idelalisib. If the toxicity does not resolve to CTC Grade \leq 2 within 2 weeks, additional doses of the interrupted drug(s) will not be administered unless the toxicity is deemed related to the subject's underlying disease in the opinion of the investigator. If the toxicity is deemed to be related to one agent (tirabrutinib or idelalisib), the subject may resume the other drug as a single agent, however, the discontinued drug may not be re-initiated on this study.

A subject who discontinues obinutuzumab for any reason other than progression may remain on study receiving the combination of tirabrutinib and idelalisib as assigned.

Subjects experiencing a related or non-related AE at any point during the study that takes longer than 2 weeks to resolve will be reviewed on a case-by-case basis by the investigator and the sponsor. Upon resolution of the AE, or in the opinion of the Investigator if the AE is considered to be well controlled and if the subject is deemed to be gaining clinical benefit from treatment with tirabrutinib and/or idelalisib, a subject may continue to receive tirabrutinib and/or idelalisib at their assigned dose or at a lower dose (and consistent with Table 6-2). The dose may subsequently be increased back to the original dose level if considered safe to do so by the treating investigator and upon approval by the sponsor.

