Stevens-Johnson Syndrome (SJS), Toxic Epidermal Necrolysis (TEN) and Drug Reaction with Eosinophilia and Systemic Symptoms (DRESS).		
Any Grade	Discontinue Idelalisib and concomitant medications that have been associated with SJS/TEN and drug reaction with eosinophilia and systemic symptoms (DRESS). Institute systemic immunosuppression per institutional standards.	-

NCI CTCAE Grade	Recommendation	
	Idelalisib	Tirabrutinib
Bowel Perforation		
Any Grade	Discontinue idelalisib.	Maintain current dose level and schedule.
Progressive Multifocal Leukoencephalopathy (PML)		
Any Grade	Withhold idelalisib until PML is excluded. Refer to section 6.6.11	-
Diarrhea		
Grade \geq 1	In the absence of evidence of infection, provide anti-diarrheal (eg, loperamide) and maintain current tirabrutinib and idelalisib dose level and schedule.	
Grade 2	Withhold idelalisib until Grade \leq 1. Consider anti-diarrheal (eg, loperamide). Resume idelalisib at previous dose level. If rechallenge results in recurrence, discontinue idelalisib. Consider addition of anti-inflammatory (eg, budesonide).	Withhold tirabrutinib until resolved to Grade \leq 1. If resolution occurs within 7 days, tirabrutinib may be reinitiated at the previous dose. If the toxicity recurs or is persistent with corticosteroid therapy, decrease to 40 mg.
Grade 3 or 4	Withhold idelalisib until resolved to Grade 1 or baseline (recovery). Rule out infectious etiology including CMV (see Section 6.2.10.1). Consider anti-diarrheal (eg, loperamide) and/or addition of anti-inflammatory agent (eg, sulfasalazine, budesonide). If toxicity persists or recurs upon repeated rechallenge, permanently discontinue idelalisib. Refer to Section 6.2.10.1 for evaluation.	Withhold tirabrutinib until Grade \leq 1. Consider anti-diarrheal (eg, loperamide) and/or addition of anti-inflammatory agent (eg, sulfasalazine, budesonide).
Hepatic Adverse Events (elevations in ALT, AST or bilirubin)		
Grade 1 (ALT/AST \leq 3 \times ULN) (Bilirubin \leq 1.5 \times ULN)	Maintain current dose level and schedule.	
Grade 2 (ALT/AST > 3-5 \times ULN) (Bilirubin > 1.5 - \leq 3 \times ULN)	Maintain current dose level and schedule. Monitor ALT, AST, ALP, and bilirubin at least 1 \times per week.	

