Grade 4	Discontinue tirabrutinib and idelalisib.	

a) CMV should be diagnosed using clinical or laboratory criteria per established institutional standard

Table 6-3. Dose Adjustment Guidelines for Subjects Receiving Obinutuzumab

NCI CTCAE Grade	Recommendation
	Toxicity attributable to obinutuzumab
HEMATOLOGICAL ADVERSE EVENTS*	
Neutropenia^a	
Grade ≤ 2 neutropenia	Maintain current dose level and schedule.
Grade 3 neutropenia	Maintain current dose level and schedule. Consider G-CSF support.
Grade 4 neutropenia (or occurrence of neutropenic fever or infection)	Delay obinutuzumab until Grade ≤ 2 (ANC ≥ 1 × 10 ⁹ /L) and/or neutropenic fever or infection is resolved; thereafter, resume at full dose. Consider G-CSF support to avoid delays. If delay is > 4 weeks, discontinue obinutuzumab.
Thrombocytopenia	
Grade ≤3	Maintain current dose level and schedule.
Grade 4	Delay obinutuzumab until Grade ≤ 3 (platelets ≥ 25 × 10 ⁹ /L); thereafter, resume at full dose. If delay is > 4 weeks, discontinue obinutuzumab, unless the Grade 4 thrombocytopenia occurred after the first 3 weekly doses.
Hemorrhage	
N/A	
Hold obinutuzumab in case of platelets < 20,000/μL. If Day 8 is delayed then skip Day 8 and administer Day 15 as previously scheduled (if symptomatic bleeding has resolved). If Day 15 is delayed then skip Day 15 dosing and administer Day 29 of obinutuzumab as scheduled.
 
At the discretion of the study investigator, for subjects who are on low molecular weight heparin (LMWH), when thrombocytopenia with platelets <20,000/μL develops, reduce the dose of LMWH or new oral anticoagulants (NOAC) used.
 
Hold tirabrutinib and obinutuzumab for clinically significant bleeding (irrespective of platelet count) until it resolves.

NON-HEMATOLOGICAL ADVERSE EVENTS	
Cutaneous	
Grade ≤2	Maintain current dose level and schedule.
Grade 3 or 4	Delay obinutuzumab until Grade ≤ 1; thereafter, may resume at full dose or discontinue obinutuzumab at investigator discretion.
Gastrointestinal Inflammation/Diarrhea	
Grade ≤1	Maintain current dose level and schedule.
Grade 2	Maintain current dose level and schedule.
Grade 3	Hold idelalisib and obinutuzumab until subject is sufficiently stable to receive further treatment; thereafter maintain full dose and schedule. If recurrent with rechallenge, consider treatment with tirabrutinib alone.

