Grade 4	Delay all study medication until subject is sufficiently stable to receive further treatment; if recurrent with rechallenge, consider treatment with tirabrutinib alone.

NCI CTCAE Grade	Recommendation
	Toxicity attributable to obinutuzumab
Hepatic Adverse Events (elevations in ALT, AST, or bilirubin)	
Grade ≤1 (ALT/AST≤3×ULN) (Bilirubin≤1.5×ULN)	Maintain current dose level and schedule.
Grade 2 (ALT/AST>3-5×ULN) (Bilirubin>1.5-≤3×ULN)	Maintain current dose level and schedule.
Grade 3 (ALT/AST>5-20×ULN) (Bilirubin>3-10×ULN)	Withhold all study medication. Monitor ALT, AST, ALP, and bilirubin at least 1× per week until all abnormalities are Grade ≤ 1 or baseline. If bilirubin abnormality was Grade < 3, resume tirabrutinib and idelalisib at previous dose level, resume obinutuzumab. If bilirubin abnormality was Grade ≥ 3, discontinue idelalisib and obinutuzumab.
Grade 4 (ALT/AST>20×ULN) (Bilirubin>10×ULN)	Withhold all study medication. Monitor ALT, AST, ALP, and bilirubin at least 1× per week until all abnormalities are Grade ≤ 1 or baseline. If bilirubin abnormality was Grade < 3, resume tirabrutinib. If bilirubin was grade 4, discontinue all study medication.
Pneumonitis	
Grade ≤1	Maintain current dose level and schedule.
Grade 2	Withhold all study medication until Grade ≤ 1, consider systemic corticosteroids. May consider resuming therapy with tirabrutinib alone
Grade ≥3	Delay obinutuzumab as necessary to ensure subject is sufficiently stable to receive further treatment; thereafter maintain full dose and schedule or discontinue obinutuzumab at investigator discretion.
Hypersensitivity	
Any Grade	Stop the infusion and discontinue obinutuzumab treatment (see section 6.6.2)
OTHER NON-HEMATOLOGICAL ADVERSE EVENTS	
Grade ≤2	Maintain current dose level and schedule.
Grade ≥3	If felt to be related to obinutuzumab, delay obinutuzumab as necessary to ensure subject is sufficiently stable to receive further treatment; thereafter maintain full dose and schedule or discontinue obinutuzumab at investigator discretion.

Abbreviations: ALP alkaline phosphatase, ALT alanine aminotransferase, AST aspartate aminotransferase, ANC absolute neutrophil count, CTCAE Common Terminology Criteria for Adverse Events, G CSF granulocyte colony stimulating factor, NCI National Cancer Institute, ULN upper limit of normal

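### For Grade 3 diarrhea, Protocol Table 6-3 lets idelalisib restart on clinical stability with no recovery grade, while Table 6-2 requires Grade 1 or baseline; the Grade 4 rows differ in the same way

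*Protocol*

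**What the plan says.** Both tables are in Protocol Section 6.5. By its title, Table 6-2 covers adjustments related to idelalisib and/or tirabrutinib. Table 6-3 is titled for subjects receiving obinutuzumab, and its column header restricts it to toxicity attributed to that drug.

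For Grade 3 gastrointestinal inflammation or diarrhea, Table 6-3 reads: "Hold idelalisib and obinutuzumab until subject is sufficiently stable to receive further treatment; thereafter maintain full dose and schedule". It continues: "If recurrent with rechallenge, consider treatment with tirabrutinib alone". That is the row's only mention of tirabrutinib. At Grade 4, Table 6-3 reads: "Delay all study medication until subject is sufficiently stable to receive further treatment".

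For Grade 3 or 4 diarrhea, Table 6-2 has a column for each oral drug. For idelalisib: "Withhold idelalisib until resolved to Grade 1 or baseline (recovery"). For tirabrutinib: "Withhold tirabrutinib until Grade" ≤ 1. Table 6-2 already withholds both drugs at Grade 2, in each case until Grade ≤ 1. After that recovery its idelalisib column says "Resume idelalisib at previous dose level. If rechallenge results in recurrence, discontinue idelalisib".

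The text before the tables adds four qualifications. The tables are guidelines from which an investigator may depart, and diarrhea is not among the listed exceptions. Whether to withhold a drug not blamed for the event is left to the investigator. If toxicity has not resolved to Grade ≤ 2 within 2 weeks, "additional doses of the interrupted drug(s) will not be administered unless the toxicity is deemed related to" the underlying disease. Events lasting more than 2 weeks are reviewed individually, with any continued oral dosing to be consistent with Table 6-2.

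**The concern.** An Arm B subject takes three drugs, so Grade 3 diarrhea during the obinutuzumab period will often be hard to attribute to one of them. Table 6-3 is nominally an obinutuzumab table, yet its Grade 3 diarrhea row also directs idelalisib. Its fallback on recurrence drops idelalisib along with obinutuzumab, so the row itself treats idelalisib as a possible cause. A site that opens Table 6-3 finds a complete-looking instruction for idelalisib and has no prompt to turn to Table 6-2, which sets a stricter recovery threshold for the same event.

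What is at stake is re-exposure to idelalisib before recovery. Protocol Section 6.6.3 describes severe idelalisib-associated diarrhea as responding poorly to antimotility agents, with median time to resolution between 1 week and 1 month across trials after interruption. The documents do not say how long the interval between clinical stability and Grade 1 would be. No efficacy analysis is involved.

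**Working it through.** The documents state no figure for this point, so the check is a row-by-row comparison followed by a rough count of subjects.

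**Step 1. The rows side by side**

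| Event | Drug | Table 6-2 | Table 6-3 |
|---|---|---|---|
| Grade 3 diarrhea | idelalisib | withhold to Grade 1 or baseline | hold until stable enough, then full dose; no grade |
| Grade 3 diarrhea | tirabrutinib | withhold to Grade ≤ 1 | no statement on holding |
| Grade 4 diarrhea | idelalisib | withhold to Grade 1 or baseline | delay until stable enough; no grade |
| Grade 4 diarrhea | tirabrutinib | withhold to Grade ≤ 1 | delay until stable enough; no grade |

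The recovery threshold differs for idelalisib at Grade 3 and for both oral drugs at Grade 4. The absence of a tirabrutinib hold is confined to Grade 3.

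**Step 2. Does the gap include a grade that Table 6-2 excludes?** Yes, Grade 2. A subject whose diarrhea has eased from Grade 3 to Grade 2 could be judged stable enough under Table 6-3. Under Table 6-2, Grade 2 is itself a reason to withhold idelalisib.

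**Step 3. Does Section 6.5 close the gap?** The two-week rule is satisfied at Grade 2 and sets no restart grade inside the first two weeks. The individual review tied to Table 6-2 starts only after two weeks. Neither says which table applies when attribution is shared.

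**Step 4. Is the difference explained?** No reason is given. The Grade 3 and 4 hepatic rows are nearly identical in the two tables, and both use Grade ≤ 1 or baseline. Elsewhere Table 6-3 names Grade ≤ 1 (Grade 3 or 4 cutaneous events, Grade 2 pneumonitis).

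**Step 5. How many subjects?** Inputs, all from the Protocol:
- Section 1.4: 32 subjects treated with idelalisib 150 mg twice daily plus obinutuzumab; Grade ≥ 3 diarrhea 6%. Since 1/32 = 3.1%, 2/32 = 6.25% and 3/32 = 9.4%, this is 2 subjects.
- Section 1.3.4: 23 subjects on tirabrutinib plus idelalisib. Diarrhea is not listed among the Grade ≥ 3 events seen in more than 1 subject, so it occurred in at most 1.
- Section 8.9: 30 subjects planned in Arm B.
- Section 6.6.3: median onset of Grade 3 or 4 diarrhea or colitis on idelalisib, 7.1 months (range 0.5 to 29.8).

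Exact (Clopper-Pearson) 95% limits, scaled to 30 subjects:
- 2/32 = 6.25% (0.77% to 20.81%); × 30 = 1.9 (0.2 to 6.2).
- 1/23 = 4.35% (0.11% to 21.95%); × 30 = 1.3 (0.03 to 6.6).
- 0/23: upper limit 14.8%; × 30 = 4.4.

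Onset: 7.1 × 30.4375 / 7 = 30.9 weeks. The last obinutuzumab dose, at Week 21 Day 1, is 20 weeks after the first, so the median onset falls after obinutuzumab has ended.

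These counts cover Grade ≥ 3 diarrhea of any attribution. The relevant subset is smaller: events while obinutuzumab is being given, of shared or uncertain attribution, managed from Table 6-3 alone, and restarted above Grade 1.

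**The case against.** The strongest reply is that attribution already routes the subject. The and/or in Table 6-2's title brings in any event where an oral drug is implicated, even jointly. If idelalisib is suspected, Table 6-2 applies; if it is not, Section 6.5 leaves it to the investigator. Clinical stability does not direct a restart at Grade 2, waiting for Grade ≤ 1 satisfies both tables, and both are guidelines. Section 7.5 sends toxicity-management questions to the Medical Monitor, Sections 6.2.10.1 and 6.6.3 set out the diarrhea work-up, and Sections 3.2 and 6 provide for steering committee safety review.

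Much of this stands. It limits the problem to shared or uncertain attribution at a site reading Table 6-3 alone, and it makes an unsupervised early restart less likely. It does not remove the mismatch: Table 6-3 itself directs idelalisib, none of the safeguards sets a restart grade, and no sentence ranks the tables.

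The objection succeeds on tirabrutinib. A reader might infer that Table 6-3 tells sites to continue tirabrutinib through Grade 3 diarrhea. It does not; the row is silent. Section 6.5 gives discretion over a drug not blamed for the event, and Section 1.6 reports no Grade 3 or higher diarrhea attributed to tirabrutinib in the 90-subject monotherapy study. Not holding it for diarrhea attributed to obinutuzumab is defensible.

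**Conclusion.** The inconsistency is real but narrow. For an Arm B subject still on obinutuzumab with Grade 3 diarrhea of shared or uncertain attribution, Table 6-3 permits a full-dose idelalisib restart without a recovery grade, and Table 6-2 does not. At Grade 4 the same threshold mismatch applies to both oral drugs. The silence on tirabrutinib at Grade 3 is a secondary observation.

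Few subjects are likely affected. The point estimates, about 1.9 and at most 1.3 of 30, count events of any attribution, so the relevant subset is smaller. A reader might infer from the upper confidence limits that 6 to 7 of 30 subjects are at risk. The documents do not support that: those limits reflect samples of 32 and 23 and the wider group. The sources are also indirect. The 32 subjects had untreated CLL, took three times this trial's daily idelalisib dose (300 mg against 100 mg) and had a median exposure of only 9 weeks; the 23 had various lymphoid malignancies and received no obinutuzumab. The triplet's rate is unknown.

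Nor do the tables conflict on idelalisib dose level: Table 6-2 sets no reduced idelalisib dose for diarrhea. The disagreement is only about when to restart.

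This is a cheap improvement for patient safety, of minor severity.

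**What to change.** In both the Grade 3 and Grade 4 diarrhea rows of Table 6-3, limit the stability criterion to obinutuzumab. State in both rows that idelalisib and tirabrutinib are withheld and resumed per Table 6-2 (Grade ≤ 1 or baseline) whenever an oral drug may have contributed. Keep the option of tirabrutinib alone on recurrence, but only after that recovery. Both parts are needed in both rows: adding a cross-reference to the Grade 4 row without narrowing its stability criterion would leave two restart thresholds in one row.

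The clinical cost is a slightly longer oral-drug interruption in a few subjects. The administrative cost is two table rows, by clarification letter or at the next amendment. Endpoints, sample size and SAP do not change. The documents do not say whether any subject is still receiving obinutuzumab; if none is, the wording should be corrected in any successor protocol that reuses these tables.

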The dose modification instructions focus on the types of events most commonly attributed to each of the study agents. The recommendations provided in Table 6-2, and Table 6-3 comprise only guidelines; variations from these recommendations may be warranted based on an investigator's individual judgment in considering potential risks, benefits, and therapeutic alternatives available to each subject. **The exceptions are SJS/TEN or DRESS, Grade 4 ALT/AST with Bilirubin elevation, organizing pneumonia, symptomatic (Grade \geq 2) pneumonitis, PJP infection, and bowel perforation where idelalisib must be discontinued**

Table 6-2. Dose Adjustments, Withholding and Discontinuation Related to Idelalisib and/or Tirabrutinib

NCI CTCAE Grade	Recommendation	
	Idelalisib	Tirabrutinib
HEMATOLOGICAL ADVERSE EVENTS		
Neutropenia^a		
Grade ≤ 3 Neutropenia	Maintain current dose level and schedule. Blood counts must be monitored at least weekly until Grade ≤ 2.	Maintain current dose level and schedule.
Grade 4 neutropenia (or occurrence of neutropenic fever or infection)	Withhold until resolved to Grade ≤2. Consider G-CSF support. Tirabrutinib and idelalisib may be reinitiated either together or sequentially. Blood counts must be monitored at least weekly until ANC ≤ Grade 2. If the toxicity recurs, consider discontinuing idelalisib.	Withhold tirabrutinib until resolved to Grade ≤ 2. Consider G-CSF support. If the toxicity recurs, consider a decrease in tirabrutinib to 40 mg. If toxicity persists following discontinuation of idelalisib alone, discontinue tirabrutinib as well.
Thrombocytopenia		
Grade ≤ 3 Thrombocytopenia	Withhold for clinically significant bleeding.	
Grade 4 Thrombocytopenia	Withhold tirabrutinib and idelalisib until resolved to Grade 1 or baseline (recovery). Tirabrutinib and idelalisib may be reinitiated at the previous dose. If the toxicity recurs, consider a decrease in tirabrutinib to 40 mg or discontinuing tirabrutinib. If toxicity persists following discontinuation of tirabrutinib, discontinue idelalisib as well.	
NON-HEMATOLOGICAL ADVERSE EVENTS		
Rash		
Grade ≤ 2	Maintain current dose level and schedule.	
Grade 3 or 4	Withhold tirabrutinib and idelalisib until resolved to Grade 1 or baseline (recovery). Tirabrutinib and idelalisib may be resumed and a dose reduction to tirabrutinib 40 mg may be considered if multiply recurrent. If toxicity recurs following repeated rechallenge, discontinue tirabrutinib and/or idelalisib.	

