Grade 3 (ALT/AST > 5-20 \times ULN) (Bilirubin > 3-10 \times ULN)	Withhold all study medication. Monitor ALT, AST, ALP, and bilirubin at least 1 \times per week until all abnormalities are Grade \leq 1 or baseline. If bilirubin abnormality was Grade < 3, resume tirabrutinib and idelalisib at previous dose level and resume obinutuzumab. If bilirubin abnormality was Grade \geq 3, discontinue idelalisib and obinutuzumab.	
Grade 4 (ALT/AST > 20 \times ULN) (Bilirubin > 10 \times ULN)	Withhold all study medication. Monitor ALT, AST, ALP, and bilirubin at least 1 \times per week until all abnormalities are Grade \leq 1 or baseline. If bilirubin abnormality was Grade < 3, resume tirabrutinib only. If bilirubin was Grade 4, discontinue all study medication.	

NCI CTCAE Grade	Recommendation	
	Idelalisib	Tirabrutinib
Organizing Pneumonia		
Any Grade	Discontinue idelalisib permanently. Institute supportive care as appropriate.	
Pneumonitis		
Grade 1	Withhold all study medication until resolution to baseline. May resume therapy at investigator discretion.	
Grade 2	Discontinue all study medication. Supportive care, including oxygen or mechanical ventilation, should be considered early and provided as necessary. May consider resuming therapy with tirabrutinib alone after discussion with medical monitor.	
Grade 3 or 4	Discontinue all study medication permanently, institute systemic corticosteroids and supportive care per institutional standard.	
PJP infection		
Any Grade	Discontinue idelalisib. Consider discontinuation of tirabrutinib until the infection has resolved.	
Unequivocal CMV infection^a		
Any Grade	Discontinue idelalisib. Consider discontinuation of tirabrutinib until the infection has resolved. If the benefits of resuming idelalisib are judged to outweigh the risks, consideration should be given to administering pre-emptive CMV therapy.	
Hypersensitivity		
Any Grade	Consider interrupting or discontinuing tirabrutinib treatment (see Section 6.6.2).	
OTHER NON-HEMATOLOGICAL ADVERSE EVENTS		
Grade 1	Maintain current dose level and schedule	
Grade 2	Withhold tirabrutinib and idelalisib until Grade \leq 1 or baseline. May resume idelalisib with tirabrutinib at initial or lower dose level or discontinue tirabrutinib and idelalisib at investigator discretion.	
Grade 3	Withhold tirabrutinib and idelalisib until Grade \leq 1 or baseline. May resume idelalisib with tirabrutinib at lower dose level or discontinue tirabrutinib and idelalisib at investigator discretion.	

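### Table 6-3 treats Grade 3 or higher pneumonitis less strictly than Grade 2, and Table 6-2 is stricter on obinutuzumab at Grades 1 and 3–4

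*Protocol*

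**What the plan says.** Protocol Section 6.5 holds two dose-modification tables. Table 6-2 is titled for idelalisib and/or tirabrutinib. Table 6-3 covers subjects on obinutuzumab, and its column heading limits it to toxicity attributed to that drug.

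Pneumonitis in Table 6-3:
- Grade 1 or lower: dosing continues unchanged.
- Grade 2: all study drugs are withheld until Grade 1 or lower, with the advice "consider systemic corticosteroids. May consider resuming therapy with tirabrutinib alone".
- Grade 3 or higher: "Delay obinutuzumab as necessary to ensure subject is sufficiently stable to receive further treatment; thereafter maintain full dose and schedule or discontinue obinutuzumab", at the investigator's discretion.

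Pneumonitis in Table 6-2:
- Grade 1: "Withhold all study medication until resolution to baseline. May resume therapy at investigator discretion".
- Grade 2: all study drugs are discontinued; tirabrutinib alone may be considered again after talking to the medical monitor.
- Grade 3 or 4: "Discontinue all study medication permanently, institute systemic corticosteroids and supportive care per institutional standard".

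The text before the tables sets their status. For an event attributed to a study drug, the investigator's "discretion will be used to determine if the drug not attributed to the AE will be withheld". The tables "comprise only guidelines; variations from these recommendations may be warranted". A short list of exceptions is binding. It includes symptomatic (Grade 2 or higher) pneumonitis, but it obliges the site to stop idelalisib only.

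**The concern.** A toxicity table should not become more lenient as the event becomes more severe. Here the Grade 2 row stops every drug, sets a recovery threshold and prompts corticosteroids. The next row up does none of these and expressly allows obinutuzumab to return at full dose. A site looking up a Grade 3 or 4 case finds weaker direction than for a Grade 2 case.

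The two tables also differ on obinutuzumab. For a severe Arm B event that cannot be assigned to one drug, one table points to stopping everything for good and the other permits further full-dose infusions. Subject safety and uniform handling of obinutuzumab across sites are at stake.

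**Working it through.** No sample size, error rate or other planned figure bears on this point, so the check is a comparison of texts.

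**1. Obinutuzumab action by grade**

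| Pneumonitis grade | Table 6-2 | Table 6-3 | Stricter |
|---|---|---|---|
| 1 | Withhold until baseline | Continue | 6-2 |
| 2 | Discontinue; only tirabrutinib named for restart | Withhold until Grade 1 or lower; only tirabrutinib named for restart | Nearly the same in effect |
| 3–4 | Discontinue permanently | Delay until stable, then full dose, or discontinue | 6-2 |

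**2. Does Table 6-2 reach obinutuzumab?** Yes. Its hepatic Grade 3 row also withholds all study medication. If the bilirubin abnormality was below Grade 3, it then tells the site to "resume tirabrutinib and idelalisib at previous dose level and resume obinutuzumab"; otherwise idelalisib and obinutuzumab are discontinued. The collective term therefore includes obinutuzumab.

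**3. The step inside Table 6-3.** From Grade 2 to Grade 3 or higher, four elements weaken: the scope falls from all drugs to one, the recovery grade disappears, the corticosteroid prompt disappears, and full-dose obinutuzumab becomes an explicit option. Both rows sit under the same attribution heading, so attribution cannot explain the change.

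**4. Is this the table's general pattern?** The categories with grade steps are neutropenia, thrombocytopenia, cutaneous, gastrointestinal, hepatic, pneumonitis and other non-hematological, which makes 7. Hemorrhage and hypersensitivity have no grade steps. A higher grade carries a weaker action in pneumonitis only: 1 of 7.

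**5. Likely origin (inference).** The catch-all row for other non-hematological events at Grade 3 or higher reads "If felt to be related to obinutuzumab, delay obinutuzumab as necessary to ensure subject is sufficiently stable to receive further treatment" and then continues like the pneumonitis row. Apart from the missing opening condition, the texts match. This looks like default text that was never adapted.

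**6. Can both tables apply to one event?** Yes. Protocol Section 7.2.1 asks only for a reasonable possibility of causation, and SAP Section 7.1.3 shows that relatedness is recorded separately for each of the three drugs. An event attributed to all three falls under both tables. At Grade 1, no single obinutuzumab action satisfies both. At Grade 3–4, stopping satisfies both, but Table 6-3 alone would allow resumption. The discretion in Section 6.5 covers the drug to which the event is not attributed, so it does not settle shared attribution.

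**7. Does other text close the gap?** The binding exception covers idelalisib only. Section 6.6.7 tells sites to interrupt idelalisib for serious lung events and gives no rule for obinutuzumab.

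**8. Scale.** The nearest figure is in Protocol Section 1.4: serious pneumonitis in 6% of 32 subjects given idelalisib with obinutuzumab, or 0.06 × 32 = 1.92, about 2 subjects. That was at idelalisib 150 mg twice daily in untreated CLL, and serious is not the same as Grade 3–4. If the same rate is assumed for 30 Arm B subjects, 0.06 × 30 = 1.8, about 2 cases, and fewer once limited to cases attributed to obinutuzumab with infusions still due. This shows only that the event is plausible; it does not estimate a count for this regimen.

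**The case against.** Five points can be made for leaving the text alone.

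- **The Grade 2 row does not forbid obinutuzumab.** Withholding until recovery implies possible restart, the tirabrutinib sentence is permissive, and only the Grade 3 or higher row mentions discontinuing obinutuzumab. This stands in part. The Grade 2 row still has a recovery grade, a steroid prompt and coverage of all drugs, which the higher row lacks.
- **Full dose is the only dose.** Section 5.3.2 plans no obinutuzumab reductions. True, but the issue is whether to resume after severe pneumonitis at all, and on what recovery criterion.
- **The tables differ by cause.** The protocol describes pneumonitis mainly as an idelalisib risk, so most severe cases would fall under Table 6-2 and stop everything. This reduces how often the conflict arises. It does not explain the inversion inside Table 6-3 or settle events attributed to more than one drug.
- **The tables are guidelines, with safeguards elsewhere.** Idelalisib stops at Grade 2 or higher regardless, the oral drugs have a 2-week interruption limit, long-lasting events are reviewed with the sponsor, and a site that stops obinutuzumab at Grade 3–4 complies with both tables. All of this stands, but none of it gives a recovery threshold or stopping rule for obinutuzumab after Grade 3 or higher pneumonitis.
- **Continuing at Grade 1 is a legitimate choice.** It is, for an event attributed to obinutuzumab alone. With shared attribution, the two tables give opposite instructions.

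**Conclusion.** The concern holds. The text is wrong as written, since following it permits weaker handling of severe than of moderate pneumonitis, and it should be corrected. The defect is one inverted step in 1 of 7 graded categories of Table 6-3, plus two grade levels (1 and 3–4) at which Table 6-2 is stricter.

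The inversion needs no assumption beyond the text. The cross-table conflict matters mainly for Arm B events attributed to more than one drug or not assignable to one. Both matter only while obinutuzumab doses remain, that is, up to 8 doses over Weeks 1–21. The documents do not say whether that dosing is complete; if it is, no subject in this study is still exposed. The primary endpoint analysis is not affected.

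**What to change.** Reword the Table 6-3 row for Grade 3 or higher pneumonitis so that it is at least as strict as Grade 2. The simplest way is to adopt the permanent discontinuation of all study drugs in Table 6-2.

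For Grade 1 or lower, either align the Table 6-3 row with Table 6-2, or add one sentence stating that Table 6-2 governs whenever pneumonitis cannot be attributed to obinutuzumab alone. Notify the sites.

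The cost is two table rows, or one row and one sentence, plus a site letter. Endpoints, sample size and the SAP stay as they are.
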